7 SAMPLE AND RECRUITMENT

7.1 Eligibility Criteria

The study will recruit adult patients that are attending a remote video consultation with a healthcare professional from the pre-operative assessment clinic at Great Western Hospital, Swindon. This will include male and female participants. The study will aim to recruit patients that meet the inclusion criteria and will exclude patients that meet the exclusion criteria.

Patients that are deemed to be high-risk for difficult intubation or airway management by the preoperative assessment staff are sometimes referred to a senior anaesthetist for in-person assessment. This is a decision that is made by the pre-operative staff, often in conjunction with senior anaesthetists, and is based on their clinical reasoning. These patients will be included in the study.

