6 STUDY SETTING

The study will take place at Great Western Hospital, Swindon, and is a single centre study.

Participants will be identified via the Great Western Hospital Pre-Operative Assessment Clinic. Potential participants will be contacted by the researcher via telephone prior to their attendance at the pre-operative clinic in-order to provide the participant information (via email), check eligibility criteria and gain electronic consent using the Microsoft Forms online platform. Microsoft forms is compliant with GDPR and the Data Protection Act (2018). The consent forms will be password protected, with access granted on an individual basis to select members of the research team.

Prior to recruitment start, staff will undergo the relevant training and receive the necessary information, either remotely, or face-to-face. Pre-operative assessment staff already perform remote video airway assessments as part of their day-to-day job. Data will be collected in the pre-operative assessment clinic and in the operating theatre for the remote video assessment and the in-person assessment respectively. Both data sets will initially be recorded onto paper forms and then transcribed to a secure database, as outlined in section 5. Any paper forms will immediately be disposed of in-keeping with the hospital confidential waste policy.

Participants will be considered eligible for enrolment into this study if they fulfil all of the inclusion criteria and none of the exclusion criteria as defined in section 7.

Using Great Western Hospital is an appropriate setting for this study as it already has an operational video-calling system in place that adheres to the principles of GDPR and meets the necessary data security standards. The hospital also has a research and innovation department that is willing to review the study protocol and support the study through local feasibility approval processes.

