7.2 Sampling

7.2.1 Size of sample

A sample size calculation has been performed so that the study has a stated probability of detecting a statistically significant kappa coefficient^[11]. We used an a priori calculation with the assumption that a kappa of ≥ 0.7 could be considered good agreement. Assuming that the average proportion of positive ratings on a dichotomous question is 0.7, that the assessors are unbiased, that the two-tailed null value is 0.5, and that the pairwise kappa we wish to detect is 0.7, we would need 173 subjects. To correct for possible systemic biases, we plan to recruit 200 subjects.

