8.6 Data protection and patient confidentiality

All data will be handled in accordance with the Data Protection Act 2018 (UK implementation of the EU General Data Protection Regulation (GDPR)).

Forms completed by the pre-operative assessment staff will contain similar data to what is already being collected by the service. Basic participant demographic data (e.g. gender, age) will also be recorded. Data will be recorded on paper Case Report Forms and will be stored in a locked cabinet in the pre-operative assessment clinic, which is only accessible to delegated members of the research team. This data will then be transcribed onto a pseudo-anonymised password-protected database on the Hospital's servers, using the patient's unique study identifier. This will happen as soon as possible and the database will only be accessible to the research team. The unique study identifier will be linked to the individuals' personal data on a separate password-protected database held on the hospital's servers.

Data collected regarding the patient's in-person anaesthetic airway assessment will be recorded on paper Case Report Forms that will only include the patient's unique study identifier. This data will also be added to the password-protected database on the Hospital's servers, as above. The data will be processed in compliance with the Sponsor's data handling policy. No video footage will be stored or recorded.

Consent forms will be issued and returned electronically. This will be done using the Microsoft Forms online service which is compliant with the Health Insurance Portability and Accountability Act (HIPAA)

and with GDPR. The consent forms will only be accessible to delegated members of the research team.

Participants' airway data (transcribed from Case Report Forms) and consent forms will be stored for up to 12 months after study completion. This is to allow processing of the airway data which will form the final dataset. Once the final dataset has been transferred to Bristol University, all personal data will be deleted.

The final dataset will be uploaded to the Bristol Research Data Service and will be accessible via the Bristol Research Data Repository (https://data.bris.ac.uk/data/). The data will be anonymised and stored for 10 years to allow further analysis. After this period the data will be deleted. Participants will be informed of this intention via the PIS and will be required to consent to this to be included in the study.

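### The protocol does not require the in-person airway reading to be recorded without sight of the video findings, so the two readings compared by kappa may not be independent

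*Protocol*

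**What the plan says.** Protocol section 6 fixes where the two readings are made: "Data will be collected in the pre-operative assessment clinic and in the operating theatre for the remote video assessment and the in-person assessment respectively". Section 7.2.2 expects several weeks between them, with video first. Section 5 compares the two readings by kappa for each airway measurement, and this is the only comparison described.

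The video reading builds on existing practice. Sections 5 and 6 say that clinic staff already assess airways by video. Section 8.6 adds: "Forms completed by the pre-operative assessment staff will contain similar data to what is already being collected by the service".

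Section 7.1 says that patients thought by pre-operative staff to be at high risk of a difficult airway are "sometimes referred to a senior anaesthetist for in-person assessment". It continues: "This is a decision that is made by the pre-operative staff, often in conjunction with senior anaesthetists". These patients are included.

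Sections 5 and 8.6 keep the clinic's paper forms in a locked cabinet, limit the database to the research team, and put only the study identifier on the in-person form.

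Section 7.2.1 assumes, for the sample size, "that the assessors are unbiased". It raises the calculated 173 subjects to 200 as an allowance for bias. No section says whether the anaesthetist may know the video result when completing the study form.

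**The concern.** Kappa tells us whether video can stand in for an in-person look only if the second reading is made independently of the first. An anaesthetist who knows what was recorded on video may settle on the same category, above all for graded judgements such as Mallampati. Agreement then rises although video is no more accurate.

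The expected direction favours the conclusion that video is comparable. It also works against the part of section 3 that predicts discordance for mouth opening and thyromental distance, because copied values would hide it.

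This is a matter of study conduct, so it belongs in the protocol. Once the forms are filled in, no analysis can restore independence. Without a record of who knew what, readers cannot judge how far independence was lost.

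**Working it through.** **Inputs from section 7.2.1.** Null kappa: "that the two-tailed null value is 0.5". Target: "the pairwise kappa we wish to detect is 0.7". Positive ratings: "Assuming that the average proportion of positive ratings on a dichotomous question is 0.7". Required number: 173; planned: 200. Significance level and power are not given as numbers; I assume 5% two-sided and 80%.

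**Reproducing 173.** The goodness-of-fit method (Donner–Eliasziw) for two raters and a binary rating, with π = 0.7, uses three cells:
- both positive: π² + κπ(1−π)
- discordant: 2π(1−π)(1−κ)
- both negative: (1−π)² + κπ(1−π)

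At κ = 0.5 these are 0.595, 0.210 and 0.195. At κ = 0.7 they are 0.637, 0.126 and 0.237.

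Σ(difference²/null cell) = 0.00296 + 0.03360 + 0.00905 = 0.04561.

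n = (1.960 + 0.842)² / 0.04561 = 7.849 / 0.04561 = 172.08, rounded up to 173. The sample size is therefore not in dispute.

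**Effect of copying.** Assume that a share f of in-person readings equal the video reading, and that the rest are independent of it with true kappa κ and equal margins. Chance agreement is unchanged at 0.7² + 0.3² = 0.58. Observed agreement becomes f + (1−f)p, where p is the agreement among the rest. Hence expected kappa = f + (1−f)κ.

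The test's noncentrality is λ = n × 0.04561 × ((expected kappa − 0.5)/0.2)². With κ = 0.5, the study's own null:

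| f (assumed) | Expected kappa | λ, n = 173 | P(reject 0.5), n = 173 | λ, n = 200 | P(reject 0.5), n = 200 |
|---|---|---|---|---|---|
| 0 | 0.50 | 0 | 5% | 0 | 5% |
| 5% | 0.525 | 0.12 | 6% | 0.14 | 7% |
| 10% | 0.55 | 0.49 | 11% | 0.57 | 12% |
| 20% | 0.60 | 1.97 | 29% | 2.28 | 33% |
| 40% | 0.70 | 7.89 | 80% | 9.12 | 86% |

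These are two-sided probabilities. At f = 0 only about 2.5% lies on the favourable side.

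**Cross-check.** With the large-sample variance of kappa, the chance of rejecting upwards at n = 173 is 5.1%, 9.5%, 27% and 84% for the four non-zero shares. The pattern is the same.

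**What the extra 27 subjects do.** 200 − 173 = 27 more pairs narrow the interval around a shifted kappa. In every row with f above zero, a wrong rejection becomes slightly more likely.

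**The case against.** A reader might infer that the anaesthetist is unblinded, that patients are referred because of the video findings, and that agreement is therefore inflated. The documents do not support any of these as fact.

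- **Silence is not unblinding.** The protocol says nothing on the point. The flow chart could not be read in the text available, and the content of the staff training is not described.
- **Referral.** Section 7.1 rests it on high-risk status and clinical reasoning, which may include history. It does not say that the senior anaesthetist also makes the theatre reading. A theatre reading anchored on an earlier in-person examination moves towards that examination, not necessarily towards the video result, so referral alone could move kappa either way.
- **Storage limits.** A theatre anaesthetist outside the research team would not ordinarily see the study's video form. Section 5 also says that clinic staff collect additional airway data for the study, so some of the six tests may have no routine entry to copy. A single f for all measurements is a simplification.
- **Size.** At small f the effect is small. Section 7.2.1 also treats kappa of at least 0.7 as good agreement. By that yardstick, with true kappa 0.5 and f = 20%, a simulation puts the observed value at 0.7 or above in only about 6% of studies of 173 pairs.

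All of this limits how strongly the point can be put. It does not close the gap. The storage rules are confidentiality measures and reach neither the clinical record nor a conversation about a referral. The assumption of unbiased assessors means equal margins in the sample-size formula; it is not a procedure.

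**Conclusion.** The point holds as a gap in the protocol: the in-person study reading is not required to be made without the video findings, and the text describes plausible routes by which they could be known. The expected effect is a higher kappa, favourable to video for most tests and masking the discordance predicted for two of them.

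The size cannot be taken from the documents. It runs from negligible (expected kappa 0.525 at f = 5%) to decisive (0.70, the study's own target, at f = 40%). This assumes exact copying, equal margins, 70% positive ratings and true kappa 0.5. That anaesthetists read the routine record, and that referral reflects the video findings, are reasonable inferences but not stated facts. The gap is worth closing before recruitment, because it touches the only main comparison and cannot be repaired afterwards.

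**What to change.** 1. In sections 5 and 6, state that, where practicable, the anaesthetist completes the study airway form before consulting the video airway findings, and that no clinical information is withheld from care.
2. Add two yes/no items to the in-person form: video findings or referral reason known before completion; patient referred after the video assessment.
3. Keep all paired patients in the main analysis. Pre-state sensitivity analyses of kappa by prior knowledge and by referral status, noting that these subsets may differ in case mix.

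The main analysis should not be restricted to patients whose findings were unseen. If notes are read earlier when a difficult airway is expected, that restriction would remove the difficult cases and could change kappa by itself.

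The cost is a short protocol statement, two form items and the extra analyses. Some forms will be marked as already known, and the subsets will be smaller and less precise. The sample size of 173 is unaffected.

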7.1.1 Inclusion criteria

Potential participants must satisfy the following criteria to be enrolled in the study:

- Age ≥18
- Attending a pre-operative remote video assessment clinic prior to an operation under general anaesthesia
- Owns a mobile phone device with the ability to video call

7.1.2 Exclusion criteria

Potential participants meeting any of the following criteria will be excluded from study participation:

- Age <18
- Lacking capacity to give consent
- Unwilling to give consent
- Pregnancy
- Prisoners
- Prior participation in the study
- Patient does not have access to a mobile smartphone device
- Does not speak English
- Difficultly understanding verbal or written instructions

7.2 Sampling

7.2.1 Size of sample

A sample size calculation has been performed so that the study has a stated probability of detecting a statistically significant kappa coefficient^[11]. We used an a priori calculation with the assumption that a kappa of ≥ 0.7 could be considered good agreement. Assuming that the average proportion of positive ratings on a dichotomous question is 0.7, that the assessors are unbiased, that the two-tailed null value is 0.5, and that the pairwise kappa we wish to detect is 0.7, we would need 173 subjects. To correct for possible systemic biases, we plan to recruit 200 subjects.

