7.2.2 Sampling technique

A convenience non-consecutive sampling technique will be employed with participants identified through the Great Western Hospital pre-operative clinic. Once ethical and final sponsorship approval has been granted, patient pre-operative clinic lists will be screened by the researchers. Patients that meet the inclusion criteria will be contacted by telephone to confirm inclusion/exclusion criteria, provide information, given the opportunity to ask questions and gain electronic consent.

There will be an estimated delay between the two airway assessments of several weeks (time taken from pre-operative video airway assessment to operation). However, given that anatomical changes to patient airways do not tend to occur acutely in a stable outpatient population this is unlikely to affect results.

Generalisability

As patients are being recruited through outpatient elective pre-operative lists, the findings may not be generalisable to unwell or unstable inpatients undergoing tracheal intubation. However, the researchers do not foresee this subgroup of patients to be the focus of future remote video airway assessments, as inpatients have the opportunity for a face-to-face assessment by an anaesthetist.

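### Recruiting 200 instead of 173 cannot correct systematic rater bias; in effect the extra 27 are the only allowance for incomplete pairs

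*Protocol*

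**What the plan says.** Protocol section 7.2.1 sizes the study on a kappa coefficient for a dichotomous rating. Its inputs are:

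- "the average proportion of positive ratings on a dichotomous question is 0.7";
- "that the assessors are unbiased";
- "that the two-tailed null value is 0.5";
- "that the pairwise kappa we wish to detect is 0.7, we would need 173 subjects".

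The aim is that "the study has a stated probability of detecting a statistically significant kappa coefficient", but the section gives no figure for that probability or for the significance level. It then raises the target with one sentence: "To correct for possible systemic biases, we plan to recruit 200 subjects". The study summary repeats 200 as the planned size. No allowance for incomplete data appears anywhere in the protocol.

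Section 5 names kappa, calculated for each airway measurement, as the comparison between the two assessors. Section 7.2.2 says of the timing: "There will be an estimated delay between the two airway assessments of several weeks". Participants may withdraw at any time (sections 5 and 7.3.2). Section 4.1 makes the frequency of tests that cannot be assessed adequately by video an objective, and section 2.2 expects poor lighting often to impair assessment of the mouth.

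**The concern.** The calculation assumes no bias between assessors, and the next sentence offers 27 more patients as the correction if there is some. Sample size cannot do that. If non-specialists on video rate a different proportion positive from anaesthetists in theatre, the kappa being estimated is itself lower, and more patients only estimate that lower value more precisely. The same holds for any other bias the sentence may have in mind.

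Two things are at stake. First, the protocol recognises a threat to its main question and records it as dealt with when it is not. Second, the only surplus over 173 is assigned to that purpose, while the protocol's own account of the study makes lost pairs likely and gives them nothing.

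**Working it through.** **1. Reproduce 173.** Inputs from section 7.2.1: p = 0.7 (q = 0.3), null kappa 0.5, alternative kappa 0.7, two-tailed. Assumed, because not stated: alpha 5% and power 80%. With two unbiased raters the cell probabilities are p² + κpq (both positive), 2pq(1 − κ) (discordant) and q² + κpq (both negative).

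- κ = 0.5: 0.595, 0.210, 0.195
- κ = 0.7: 0.637, 0.126, 0.237

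The goodness-of-fit formula is n = (z₀.₉₇₅ + z₀.₈₀)² / Σ[(P₁ − P₀)²/P₀].

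- Sum: 0.00296 + 0.03360 + 0.00905 = 0.0456
- n = (1.960 + 0.842)² / 0.0456 = 172.1, rounded up to **173**

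This matches exactly. Other choices do not: one-sided 80% gives 136, two-sided 85% gives 197, two-sided 90% gives 231, and a Wald-type formula at two-sided 80% gives 158.

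**2. What the extra 27 do.** The large-sample variance of kappa (per subject) is (1 − κ)[(1 − κ)(1 − 2κ) + κ(2 − κ)/(2pq)]. At κ = 0.7 and p = 0.7 this is 0.3 × (−0.12 + 2.167) = 0.614.

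- Standard error at 173: √(0.614/173) = 0.060
- Standard error at 200: √(0.614/200) = 0.055
- Power, Φ(√(0.0456n) − 1.960): 80% at 173 and about 86% at 200

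The expected kappa does not move.

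**3. What rater bias does.** The positive rates below are assumptions, because the protocol gives none.

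*Ceiling.* With positive rates a and b, the highest possible kappa is (1 − |a − b| − pₑ)/(1 − pₑ), where pₑ = ab + (1 − a)(1 − b).

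| a vs b | pₑ | Highest kappa, any n |
|---|---|---|
| 0.70 vs 0.60 | 0.54 | 0.78 |
| 0.70 vs 0.55 | 0.52 | 0.69 |
| 0.70 vs 0.50 | 0.50 | 0.60 |

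*Expected value.* Under an assumed latent-normal model, set to give kappa 0.70 when both raters are at 70% positive, the in-person rate stays at 70% and the video rate shifts. The n needed against a null of 0.5 uses the Wald-type formula, which gives 158 without bias.

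| Video positive | Expected kappa | n needed |
|---|---|---|
| 65% | 0.69 | 166 |
| 75% | 0.68 | 201 |
| 60% | 0.66 | 224 |
| 80% | 0.63 | 416 |

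Even read as a power margin, 27 extra subjects on a base of 173 go only as far as a small shift.

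**4. Lost pairs.** Kappa needs both ratings, so 173 is a count of complete pairs for each measurement. From 200, the tolerable loss is 1 − 173/200 = **13.5%**. The loss rates below are assumptions. Power uses the formula in step 2, and recruits needed are 173/(1 − loss).

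| Loss | Pairs from 200 | Power | Recruits needed for 173 pairs |
|---|---|---|---|
| 0% | 200 | 86% | 173 |
| 10% | 180 | 82% | 193 |
| 13.5% | 173 | 80% | 200 |
| 20% | 160 | 77% | 217 |
| 30% | 140 | 71% | 248 |

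**The case against.** The best defence is that the sentence means a power margin in case the unbiased-assessor assumption fails, and such a margin has some effect. At an expected kappa of 0.68, the step 1 formula (approximate here, since it assumes equal positive rates) gives power of about 72% at 173 and 78% at 200. That stands, so a reader who infers that the extra patients achieve nothing goes too far. But the sentence claims to correct bias, no calculation supports a margin, and 27 patients spent on that margin are not also available for lost pairs.

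Three other strong readings are not supported:

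- **That 173 is miscalculated or 200 too few.** The 173 reproduces, and 200 is enough if no measurement loses more than 13.5% of pairs. The protocol gives no loss rate, so no shortfall can be asserted.
- **That bias would go unseen.** Systematic disagreement lowers kappa, so the planned analysis would register it as poorer agreement. What kappa alone does not give is its source or direction.
- **That assessors are not identified on the forms.** Section 8.6 describes theatre records as "paper Case Report Forms that will only include the patient's unique study identifier", but this limits patient-identifying data. It is not a list of fields, and the forms are not shown.

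It is also fair to say that comparisons of marginal rates, and the handling of tests that cannot be assessed, often sit in a statistical analysis plan, which may exist here. Their absence is not the fault. The fault is that the protocol names the bias and states a remedy that cannot work.

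**Conclusion.** The reason given for moving from 173 to 200 is wrong as written. The numbers themselves contain no arithmetic error, so this is a fault of rationale and allowance. The increase cuts the standard error of kappa from about 0.060 to 0.055 and raises power from 80% to about 86% if every pair is complete. It leaves any systematic difference between raters as it was. Since no other allowance exists, the 27 in effect serve as cover for incomplete pairs, up to 13.5% per measurement. Beyond that, power falls below 80%, to about 77% at 20% loss and 71% at 30%.

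These figures rest on 80% power and two-sided 5%, both inferred from the exact match, on the protocol's 0.7 positive rate, and on loss rates chosen for illustration. The bias illustrations rest on assumed positive rates and, for expected kappa, on a latent-normal model.

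**What to change.** 1. In section 7.2.1, delete the bias rationale. Suggested text: 200 patients are recruited so that at least 173 complete pairs remain for each measurement, allowing up to 13.5% incomplete pairs; at 20% and 30% incomplete, power is about 77% and 71%. State the power and significance level behind the 173, which appear to be 80% and two-sided 5%.
2. Beside each kappa in section 5, report the paired difference between video and in-person ratings with a 95% CI: a difference in proportions for dichotomous tests, a marginal homogeneity comparison for ordered classes, and a mean difference if distances are recorded. This measures the bias that sample size cannot remove, and it uses the same paired data.

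The cost is a few sentences and a short table. No extra patients are needed.
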